5.1 Imputation rules

5.1.1 Study drug

Not applicable.

5.1.2 AE date imputation

Imputation of partial AE start dates will follow the general Novartis rules for imputation of AE start dates. Missing or partial AE end dates will not be imputed.

5.1.3 Concomitant medication date imputation

Concomitant medication date imputation will follow the general Novartis rules for imputation of CM start and end dates.

5.2 Visit windows

When visit windows are used, all visits will be re-aligned, i.e., they will be mapped into one of the visit windows. E.g., if the Day 4 visit of a patient is delayed and occurs on Day 7, say, it will be re-aligned to visit window Day 8. In the case of major deviations from the visit schedule, or due to unscheduled visits, several assessments of a patient may fall in a particular visit window (either scheduled or unscheduled). Statistical approaches to handle multiple assessments in a given visit window are specified below.

- The following rules are used to determine the window for other visits post baseline:
 - “Lower limit” = “upper limit of prior applicable visit” + 1
 - “Upper limit” = “target day of current visit” + integer part of (“target day of next applicable visit” – “target day of current visit”)/2 with the exception of Day 43
 - Upper limit for analysis visit Day 43 is day 50

Based on the different assessments [Table 5-1](#) describes the analysis visit window mapping. Repeat and/or unscheduled visits (which will be numbered in the database according to new NCDS standards) will be mapped for analysis purposes in the same way. If there are multiple measurements within an analysis window, the conventions defined in [Table 5-2](#) will be used to determine the appropriate measurement to be selected for analysis.

The mapped visits will be used in the by visit analyses. However, the listings will show the collected data regardless of used in the by visit analyses.

Table 5-1 Analysis visit windows based on study day and time

Analysis Visit	Analysis timepoint	Vital signs	Weight/Height	Blood chemistry/ Hematology	Malaria blood film
Baseline	<0 h	up to 0 h	up to 0 h	up to 0 h	up to 0 h
Day 1	8 h	>0 to 16 h	-	-	>0 to 16 h

Day 2	24 h	>16 to 30 h	> 0 to 36 h	> 0 hrs to 42 h	>16 to 30 h
	36 h	>30 to 42 h	-	-	>30 to 42 h
Day 3	48 h	>42 to 54 h	> 36 to 60 h	-	>42 to 54 h
	60 h	>54 to 66 h	-	> 42 to 114 h	>54 to 66 h
Day 4	72 h	>66 to 84 h	>60 to 84 h	-	>66 to 84 h
Day 5	96 h	> 84 to 132 h	> 84 to 132 h	-	> 84 to 132 h
Day 8	168 h	> 132 h to Day 11	> 132 h to Day 11	> 114 h to Day 11	> 132 h to Day 11
Day 15	NA	Day 12 – 22	Day 12 – 22	Day 12 – 29	Day 12 – 22
Day 29	NA	Day 23 – 36	Day 23 – 36	-	Day 23 – 36
Day 43	NA	Day 37 - 50	Day 37 – 50	Day 30 – 50	Day 37 - 50
Age 365 days	NA	-	Aged between 335 – 395 days	-	-

Table 5-2 Rules for flagging variables

Timing of measurement	Type of data	Rule
Baseline	All data	The last measurement made prior to and including administration of the first dose of study treatment – note this may include measurements taken on the day of randomization. If a patient did not receive any dose of study treatment then the IRT date for the first study drug will be used.
Post-baseline efficacy	All data	The measurement closest to the target day/time will be used. In the event that two measurements are taken equally apart (e.g. 1 day before target date and 1 day after) the first one will be used.
Post-baseline safety	Summary visit information (e.g. lab, vital signs, etc.)	The measurement closest to the target day/time will be used. In the event that two measurements are taken equally apart, the first one will be used.
Post-baseline safety	Notable abnormalities (e.g. lab)	The most extreme measurement in the window will be used. Note this means a patient can have a notably high and notably low measurement within a window

5.3 AEs coding/grading

Adverse events are coded using the Medical dictionary for regulatory activities (MedDRA) terminology.

5.4 Laboratory parameters derivations

The following table shows the direction of interest when analyzing worst case values within core period for laboratory shift tables. If the direction of interest is given as "High" the maximum value will be calculated and used as worst value, if the direction is given as "Low" the minimum value will be taken, and if it is given as "Low and high", both the minimum value and the maximum value will be calculated and presented in shift tables.

Table 5-3 Directions of interest for worst case value for laboratory parameters

Laboratory test group	Parameter	Directions of interest for worst case value
Hematology	Hemoglobin	low
Hematology	Hematocrit	low
Hematology	Reticulocytes	high
Hematology	RBC	low
Hematology	WBC	low and high
Hematology	Basophils	high
Hematology	Eosinophils	high
Hematology	Lymphocytes	low and high
Hematology	Monocytes	high
Hematology	Neutrophils	low and high
Hematology	Platelets	low
Hematology	Bands	Not applicable
Hematology	Differential other	Not applicable
Blood chemistry	Sodium	low and high
Blood chemistry	Potassium	low and high
Blood chemistry	Magnesium	low and high
Blood chemistry	Glucose	low and high
Blood chemistry	Creatinine	high
Blood chemistry	AST	high
Blood chemistry	ALT	high
Blood chemistry	Total bilirubin	high

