5.2 Exclusion criteria

Subjects meeting any of the following criteria are not eligible for inclusion in this study:

1. Head circumference $< - 2$ SD z-score in cm following WHO age and sex-specific reference curves (suspicion of microcephaly) (See [Section 16.1 Appendix 1](#))
2. Severe malnutrition (body mass index (BMI) less than 70% of median normalized WHO reference weight)
3. Presence of severe malaria (according to WHO 2015 definition - See [Section 16.4 Appendix 4](#))
4. Hemoglobin < 7 g/dL
5. HIV status:
 - in Cohort 1 : patient's or patient's mother's current treatment with ARV
 - in Cohort 2 : Mother's known HIV positive status at patient's birth or mother's current treatment with ARV
6. Presence of the following signs of a critical condition: apnea-bradycardia, sustained bradycardia, tachycardia, desaturation, hypotension, hypothermia; or other severely

deteriorated general condition (based on IMCI criteria in sick infants, WHO 2005 - See [Section 16.5 Appendix 5](#))

7. Presence of any clinically significant neurological condition:
 - any episode of convulsion during the present illness (in keeping with the IMCI list of general danger signs)
 - known neurological disorders (e.g. chronic seizure disorders, cerebral palsy)
8. Presence of clinically significant abnormality of the hepatic and renal systems
9. History of malabsorption or previous gastrointestinal surgery, or history of radiation therapy that could affect drug absorption or metabolism, or any other disorder or history of a condition that could interfere with drug absorption, distribution, metabolism, or excretion
10. Patients unable to swallow or whose drinking is impaired
11. Known hypersensitivity of the patient or either patient's parent to artemether, lumefantrine, any of the excipients of Coartem®/Riamet® Dispersible tablet, or to drugs of similar chemical classes
12. Known family history of congenital prolongation of the QT_c interval or sudden death or with any other clinical condition known to be associated with prolongation of the QT_c interval such as history of symptomatic cardiac arrhythmias, with clinically relevant bradycardia or with severe cardiac disease
13. Disturbances of electrolyte balance (e.g. hypokalemia or hypomagnesemia) - See [Section 16.1 Appendix 1](#) as an example for reference
14. Presence of any age-adjusted clinically or hematologically relevant laboratory and blood chemistry abnormalities

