8.4.1 Laboratory evaluations

[figure not shown]
At each site, a local laboratory (validated/accredited) will be used for analysis of all specimens collected, i.e., for hematology and blood chemistry (for either PCR [parasite identification and resistance markers], or PK measurements, a central reference laboratory will be used).

All specimens will be processed and analyzed in the local laboratory. If any results are of clinical concern, a repeat sample will be collected at the next scheduled visit, while remaining within the overall blood volume limit for the patient ([Howie 2011](#)).

| Test Category | Test Name |
|---------------|--|
| Hematology | Hemoglobin, hematocrit, red cell count (RBC and reticulocytes), white blood cell (WBC) count with differential (absolute value preferred, %s are acceptable) (Basophils, Eosinophils, Lymphocytes, Monocytes, Neutrophils, Bands, Other), and platelet count |
| Chemistry | sodium, potassium, magnesium, glucose, creatinine, AST (SGOT), ALT (SGPT), and total bilirubin will be measured |
| Urinalysis | Not applicable |

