* In sleep, infant heart rates may drop significantly lower, but if perfusion is maintained, no intervention is required

For information only, Premature : Heart rate (beats/min): 120-170*; Blood pressure (mm Hg): 55-75/35-45; Respiratory rate (breaths/min): 40-70

Reference ranges for magnesium are presented in [Table 16-2](#) and for potassium in [Table 16-3](#) (adapted from [Hay et al 2018](#)).

Table 16-2 Reference ranges for magnesium (mg/dL) by age range (male-female)

| Age | Male | Female |
|------------|---------|---------|
| 0-7 days | 1.2-1.6 | 1.2-1.6 |
| >7-30 days | 1.6-2.4 | 1.6-2.4 |
| >1 mo-2 y | 1.6-2.6 | 1.6-2.6 |
| >2-6 y | 1.5-2.4 | 1.5-2.4 |
| >6-10 y | 1.6-2.3 | 1.6-2.3 |
| >10-14 y | 1.6-2.2 | 1.6-2.2 |
| >14 y | 1.5-2.3 | 1.5-2.3 |

Table 16-3 Reference ranges for potassium (mmol/L) by age range (male-female)

| Age | Male | Female |
|------------|---------|---------|
| 0-7 days | 3.7-5.9 | 3.7-5.9 |
| >7 d-3 mo | 4.1-5.3 | 4.1-5.3 |
| >3 mo-18 y | 3.4-4.7 | 3.4-4.7 |
| >18 y | 3.5-5.0 | 3.5-5.0 |

Reference curves from WHO for head circumference are presented in [Figure 16-1](#) and [Figure 16-2](#) for males, and in [Figure 16-3](#) and [Figure 16-4](#) for females (https://www.who.int/childgrowth/standards/hc_for_age/en/).

[figure not shown]
Figure 16-1 Reference ranges for head circumference in males (0-13 weeks)

[figure not shown]
Figure 16-2 Reference ranges for head circumference in males (0-2 years)

[figure not shown]
[figure not shown]
Figure 16-3 Reference ranges for head circumference in females (0-13 weeks)

Figure 16-4 Reference ranges for head circumference in females (0-2 years)

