2.8.2 Laboratory data

All laboratory data will be listed by cohort, treatment group, subject, and visit/time and if normal ranges are available abnormalities will be flagged. Notable values will be flagged as well.

Descriptive statistics will be generated for all clinical laboratory tests performed (actual values and changes from baseline) for two groups of laboratory tests (hematology and blood chemistry) by laboratory test, cohort, treatment group and visit/time. Change from baseline will only be summarized for patients with both baseline and post baseline values and will be calculated as:

change from baseline = post baseline value – baseline value.

The following laboratory parameters will be analyzed for hematology test group: hemoglobin, platelets, white blood cell count, Reticulocytes, hematocrit, red blood cell (RBC) count, lymphocytes, lymphocytes (%), monocytes, monocytes (%), eosinophils, eosinophils (%), neutrophils, neutrophils (%), basophils, basophils (%), bands, bands (%), differential other and differential other (%).

The following laboratory parameters will be analyzed for blood chemistry test group: sodium, potassium, magnesium, glucose, creatinine, aspartate aminotransferase (AST), alanine aminotransferase (ALT), total bilirubin.

Shift tables using the low/normal/high/ (low and high) classification will be used to compare baseline to the worst value within the core period. The direction of interest for worst value within core period for each laboratory parameter is given in [Table 5-3](#).

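### The laboratory shift tables pick the raw extreme before classing it, so age-specific reference ranges could hide a mild abnormality

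*SAP*

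**What the plan says.** SAP 5.4 defines the worst value numerically: the maximum where the direction of interest is high, the minimum where it is low, and for two-sided parameters "both the minimum value and the maximum value will be calculated and presented in shift tables". SAP Table 5-3 gives a direction for 19 parameters; potassium and magnesium are both two-sided.

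SAP 2.8.2 uses that value: "Shift tables using the low/normal/high/ (low and high) classification will be used to compare baseline to the worst value within the core period". The core period runs from Day 1 to Day 43 (SAP 2.1.1). The same section says of the listings that "if normal ranges are available abnormalities will be flagged".

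Neither section names the ranges behind the shift tables. Protocol 8.4.1 says: "At each site, a local laboratory (validated/accredited) will be used for analysis of all specimens collected". The only laboratory reference ranges printed are for magnesium and potassium in Protocol Appendix 1, and exclusion criterion 13 cites that appendix only "as an example for reference". Both tables are banded by age. For magnesium, the male and female columns read "0-7 days | 1.2-1.6 | 1.2-1.6" and then ">7-30 days | 1.6-2.4 | 1.6-2.4". For potassium, the band ">7 d-3 mo | 4.1-5.3 | 4.1-5.3" lies between 3.7-5.9 (0-7 days) and 3.4-4.7 (over 3 months). Exclusion criterion 14 also treats laboratory abnormality as something judged for age.

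**The concern.** Choosing the extreme first and classing it afterwards gives the right answer when one range applies to all of an infant's samples: if any sample is below the limit, so is the minimum. When the range moves between samples, that no longer follows. A numerically lower value taken at an age with a lower limit can displace the sample that was truly low for age.

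Entry starts at 1 day of age and the core period lasts six weeks, so crossings are built into the population. With the Appendix 1 bands, every infant entering at 1-7 days has passed the 7-day limit by the Day 8 visit.

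At stake is the meaning of a normal entry in the shift table, which is the only tabulated low/normal/high count in SAP 2.8.2. The listings flag values one by one but do not count them.

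**Working it through.** The plan gives no figure to reproduce here. I applied the SAP rule literally and compared it with classing every sample first.

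**Inputs.** Ranges from Protocol Tables 16-2 and 16-3. Post-baseline samples at 24 h, 60 h, Day 8 and Day 15, with and without Day 43: SAP Table 5-1 has a Day 30-50 laboratory window, but in the extracted Protocol Table 8-1 the last chemistry mark falls under age 365 days, possibly through extraction. Three months is taken as 91 days (assumption). Each extreme is classed against the range for the age at which it was sampled.

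**Worked examples (illustrative values).**

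| Case | Samples (age in days: value) | Abnormal for age | Minimum | Maximum |
|---|---|---|---|---|
| Mg, entry 3 d | 4: 1.3; 5.5: 1.4; 10: 1.5; 17: 1.8; 45: 2.0 | 1.5 at 10 d, low (<1.6) | 1.3, normal | 2.0, normal |
| K, entry 80 d | 81: 4.5; 82.5: 4.0; 87: 4.3; 94: 3.8 | 4.0 at 82.5 d, low (<4.1) | 3.8, normal | 4.5, normal |
| K, entry 80 d | 81: 5.2; 82.5: 4.8; 87: 4.6; 94: 5.0 | 5.0 at 94 d, high (>4.7) | 4.6, normal | 5.2, normal |

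As a control, potassium pairs at 16 and 22 days (no limit crossed) gave 0 missed out of 1484 abnormal pairs on a grid. The age crossing is therefore the cause.

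**How often.** Simulated value = midpoint of the range at the sampling age + z × (range width / 3.92), so that each range holds the central 95% of a normal distribution. There is no drug effect, and the within-infant correlation is 0, 0.3, 0.5 or 0.8. An infant counts as missed if any sample is outside its age range while the raw minimum and raw maximum are each inside theirs. The spans below run over the four correlations. Rounding to one decimal matches the precision of the printed ranges; where rounded values tie, the earliest sample is used.

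| Parameter, entry age | Day 43 sample | Missed, one decimal | Missed, unrounded |
|---|---|---|---|
| Mg, 3 d | yes | 2.7-5.1% | 4.8-10.4% |
| Mg, 3 d | no | 1.7-3.9% | 3.2-8.5% |
| Mg, 10 d | yes | 0.1-0.6% | 0.5-1.8% |
| K, 3 d | yes | 1.5-3.2% | 2.1-4.2% |
| K, 30 d | either | 0% | 0% |
| K, 60 d | yes | 2.7-4.3% | 3.7-6.4% |
| K, 60 d | no | 0% | 0% |
| K, 80 d | yes | 2.7-5.4% | 3.7-7.8% |
| K, 80 d | no | 2.3-3.5% | 3.0-5.2% |

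**Expected counts, one decimal.**
- Magnesium: the Amendment 1 rationale reports 2 infants in Cohort 2.2. Even if both entered at 1-6 days, 2 × 1.7-5.1% = 0.03-0.10.
- Potassium, Cohort 1 (22 infants, entry ages not given), with Day 43: 22 × share entering at 60-80 days × 2.7-5.4%. A 25% share gives 0.15-0.30 and a 50% share gives 0.30-0.59. Only if all 22 entered in that window is it 0.59-1.19.

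**The case against.** The strongest reply is that the premise is not in the documents. No section ties an age-banded range to the shift tables, the local laboratories' ranges are not shown, and 17 of the 19 parameters have no printed range. This stands: the harm is conditional. A reader might infer that Tables 16-2 and 16-3 will be used for the shift tables, and the documents do not support that.

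A second reply is that no sentence spells out the order, and that SAP 2.8.2 includes a combined low-and-high category, which could describe an infant over several samples. But SAP 5.4 gives that wording its own meaning: both numeric extremes are computed and shown. Selecting first is the plain reading.

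Third, in the magnesium example the values only rise; the low at 10 days exists because the range steps up at 7 days. That is fair. Yet anyone using age-specific ranges has accepted such steps, and a listing using the same ranges would flag that sample as low. The table should agree with the listing.

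Fourth, a reader might take the unrounded shares, up to about 10% for magnesium, as the size. They overstate it: with values to one decimal, the shares at 3 days fall by roughly half. The model also makes about 5% of unrounded samples abnormal by construction, so these are ordinary tails and not drug signals.

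Last, other safeguards exist: flagged listings, by-visit summaries, and separate handling of grade 3 or worse values (SAP 5.5). These stand and limit the consequence.

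**Conclusion.** The point holds in conditional form. SAP 5.4 states a concrete rule, and that rule gives a wrong class for some infants if the reference ranges used depend on age. With the example ranges and one-decimal values, about 2-5% of infants entering at 1-6 days are affected for magnesium, and about 3-5% of those entering at 60-80 days for potassium when there is a Day 43 sample. The share is zero for infants who cross no limit. On plausible entry ages this is under one infant in expectation; it exceeds one for potassium only near the extreme where almost all of Cohort 1 entered in that age window.

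These figures rest on the example ranges, a normal model without drug effect, correlations of 0-0.8, and entry ages the documents do not give. A missed value lies between the limits of two age bands and is therefore mild.

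A reader might go further and infer that a safety signal would be lost or a dose decision misled. The documents do not support this: no endpoint, hypothesis or dose rule uses the shift table, and the sample remains flagged in the listings where ranges exist. This is a free improvement of minor weight.

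**What to change.** In SAP 5.4 and 2.8.2, state that each sample is classed low, normal or high against the applicable range for the infant's age on the sampling date, and that the worst value is the worst class in each direction of interest over the core period. Naming the range source in the same place would settle whether the condition applies.

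The cost is one sentence and a slightly longer derivation. Age in days is already collected (Protocol 8.2), so age at each sample can be derived. If a laboratory uses one range regardless of age, the results are unchanged.

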5.5 Vital signs and Laboratory – definition of clinically notable values

The following two tables show the clinical notable criteria for vital signs. Clinically notable ranges for laboratory parameters will be defined as values graded or worse 3 (see Table 5-6) using the Division of AIDS (DAIDS) Table for Grading the Severity of Adult and Pediatric Adverse Events (Corrected version 2.1, July 2017).

Table 5-4 Normal Vital Signs according to Age

Values below the lower limit or above the upper limit of normal will be listed as Abnormal.

Age	Heart Rate (beats/min)	Blood Pressure (mm Hg)		Respiratory Rate (breaths/min)
		Systolic	Diastolic	
0-<3 months	100-150*	65-85	45-55	35-55
3-<6 months	90-120	70-90	50-65	30-45
6-12 months	80-120	80-100	55-65	25-40

Reference: [Kliegman et al 2007](#).

* In sleep, infant heart rates may drop significantly lower, but if perfusion is maintained, no intervention is required

For information only, Premature : Heart rate (beats/min): 120-170*; Blood pressure (mm Hg): 55-75/35-45; Respiratory rate (breaths/min): 40-70

Table 5-5 Normal body temperature

Vital sign parameter	Normal range
Oral/Tympanic/rectal body temperature (°C)	>= 37.0 and <= 37.9
Axillary body temperature (°C)	>= 36.5 and <= 37.4

5.6 Historical exposure values from previous studies

Table 5-6 Reference values for PK analyses

Study	Body weight in kg (and age in days for B2306)	ART Dose (mg)	First dose Artemether C _{max} (ng/mL) n, geo-mean	DHA C _{max} (ng/mL) n, geo-mean	LUM C _{max} (µg/mL) n, geo-mean	LUM C _{168h} (ng/mL) n, geo-mean
B2306	<5 kg >28 days	20	-	18, 70.2	19, 5.2	16, 666
B2303	≥5 kg - <15 kg	20	52, 101	52, 31.7	102, 3.9	27, 212
B2303	≥15 kg - <25 kg	40	30, 105	30, 45.0	48, 6.6	4, 388
B2303	≥25 kg - <35 kg	60	9, 112	9, 57.5	9, 8.3	-

ART: artemether; LUM: lumefantrine

5.7 Statistical models

5.7.1 Primary analysis

The primary analysis is detailed in [Section 2.5](#).

The primary endpoint ART C_{max} will be displayed by cohort and treatment group using the geometric mean. The geometric mean will be calculated by deriving the mean of the log-transformed values followed by an exponential transformation, i.e. *Geometric Mean (GM) = e^{mean(log(x))}* with x = ART C_{max} of a participant.

Corresponding 2-sided 90% confidence intervals for the GM will be calculated assuming a log normal distribution of the primary endpoint. The lower and upper limits will be calculated as follows:

$$\exp(\bar{x} \pm t_{(1-\frac{\alpha}{2};n-1)} \times \frac{s}{\sqrt{n}})$$

with \bar{x} = the arithmetic mean of the log-transformed endpoint, $t_{(1-\frac{\alpha}{2};n-1)}$ = the $(1 - \frac{\alpha}{2})$ critical value of the Student's t statistic with $n - 1$ degrees of freedom, s = the standard deviation of the log-transformed endpoint, and n = the number of patients with available endpoint in the corresponding cohort and treatment group.

The logarithm to the natural base is used.

The calculation will be implemented in SAS using PROC MEANS on log data followed by an exponential transformation.

5.7.2 Key secondary analysis

The key secondary analysis is detailed in [Section 2.6](#).

The calculation of the geometric mean and the corresponding 2-sided 90% confidence intervals will be done similarly as for the primary endpoint, see [Section 5.4.1](#).

5.8 Rule of exclusion criteria of analysis sets

Table 5-7 Protocol deviations and non-PD criteria leading to exclusion from analysis sets ce values for PK analyses

Analysis Set	PD (description and ID) that causes subjects to be excluded	Non-PD criteria that cause subjects to be excluded
FAS	Informed Consent for study participation not obtained (INCL05) Plasmodium falciparum not present as parasite species at Screening visit (INCL04)	No study drug taken
SAF	Informed Consent for study participation not obtained (INCL05)	No study drug taken
PPS	Baseline Plasmodium falciparum parasite count is not ≥ 500 and $< 100,000/\mu\text{L}$ at screening visit for patients in Cohort 1 (INCL04A) Baseline Plasmodium falciparum parasite count is not ≥ 100 and $< 100,000/\mu\text{L}$ at	Not in FAS Did take less than 80% of planned study medication (see Section 2.4.1) PCR corrected cure status at Day 29 can not be defined Not classified as non-responder before Day 8, no positive blood smear parasite on Day 8

Analysis Set	PD (description and ID) that causes subjects to be excluded	Non-PD criteria that cause subjects to be excluded
	screening visit for patients in Cohort 2 (INCL04B)	onwards, and blood smear parasite result is missing at Day 29.
	Prohibited concomitant anti-malarial medication administered without experiencing ETF, LCF, LPF (PROH02)	Not classified as non-responder before Day 8, have at least one positive blood smear parasite result between Day 8 and Day 29 which cannot be determined as recrudescent or new infection based on PCR genotyping.
	Prohibited concomitant non-malaria medications with potential impact on efficacy/antimalarial activity (PROH01A)	
	Presence of another critical condition (EXCL06)	
PK		Not in FAS
		No evaluable PK parameter data available

6 References

Stepniewska K, White NJ (2006) Some considerations in the design and interpretation of antimalarial drug trials in uncomplicated falciparum malaria. *Malar J*; 5: 127.

World Health Organization (2015) Guidelines for the treatment of malaria. Third Edition.

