6.2.3 Rescue medication

The following circumstances warrant discontinuation of study treatment (during the treatment period) and the implementation of rescue medication by the investigator (Commencement of rescue medication may occur after the start of study drug and up to Day 43):

Early Treatment Failure (ETF)

- Development of danger signs or severe malaria on Day 2, Day 3, Day 4 in the presence of parasitemia.
- Parasitemia on Day 3 higher than Day 1 count irrespective of axillary temperature.
- Parasitemia on Day 4 with axillary temperature $\geq 37.5^\circ$.
- Parasitemia on Day 4 equals to or more than 25% of count on Day 1.

Late Clinical Failure (LCF)

- Development of danger signs or severe malaria on any day from Day 5 to Day 43 in the presence of parasitemia without previously meeting any of the criteria of Early Treatment Failure.
- Presence of parasitemia and axillary temperature $\geq 37.5^\circ$ on any day from Day 5 to Day 43 without previously meeting any of the criteria of Early Treatment Failure.

Late Parasitological Failure (LPF)

- Presence of parasitemia on any day from Day 8 to Day 43 and axillary temperature $< 37.5^\circ$ without previously meeting any of the criteria of Early Treatment Failure or Late Clinical Failure.

Rescue treatment involves therapy with an effective antimalarial available locally as per local medical practice or National Treatment Guidelines. Administration may be oral or parenteral depending on the subject's clinical condition. Rescue treatment will not be considered study medication. The exact rescue regimen and route of administration must be recorded on the appropriate CRF.

Patients will be monitored, either in clinic, or via home visits for the duration of treatment to ensure adherence to the rescue medication therapy. These patients will not discontinue the study (i.e., all the examinations as per the assessment schedule and all CRF for this patient will need to be completed), and they will not be replaced (unless the PK data cannot be properly analyzed due to treatment schedule discontinuation).

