2.2 Analysis sets

The Full Analysis Set (FAS) comprises all subjects that received any study drug and had *Plasmodium falciparum* present at Screening visit. Subjects will be analyzed according to the treatment(s) received as per protocol.

The Safety Set includes all subjects who received at least one dose of study treatment. Subjects will be analyzed according to the study treatment received as per protocol. The Safety Set will be used for safety analyses while FAS will be used for other analyses.

The Per-Protocol Set (PPS) is a subset of subjects of the Full Analysis Set and is characterized by the following criteria:

- did not have important protocol deviations affecting efficacy
- took at least 80% of study medication
- PCR corrected cure status at Day 29 can be defined.

Important protocol deviations for exclusion from the PPS will be identified by the clinical team before database lock.

The PK set is a subset of the Full Analysis Set who had evaluable PK parameter data.

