2.4 Treatments (study treatment, rescue medication, concomitant therapies, compliance)

2.4.1 Study treatment / compliance

Number and percentage of tablets taken will be presented by cohort and treatment group. The percentage will be calculated based on the planned number of tablets per treatment group. Both number and percentage mean, standard deviation, median, 25th and 75th percentiles, minimum, and maximum will be presented.

Planned number of tablets in a treatment group = planned number of days of dosing x number of tablets to be administered per day in that treatment group.

For example, planned number of tablets for starting dose level 2 is 3 (planned number of days of dosing) x 2 (number of tablets) x 2 (twice a day) = 12 tablets.

Percentage of tablets taken will be calculated as Number of tablets consumed/Number of tablets planned x 100.

Compliance will be categorized by < 80 % and >=80 % of tablets taken and summarized by cohort and treatment group.

Number and percentage of patients with study drug vomiting and dose replacement will be presented by cohort and treatment group.

Safety set will be used.

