2.7.2.1 PCR-corrected ACPR and uncorrected ACPR

At each visit, the ACPR rate with 95% 2-sided confidence intervals will be provided using the Clopper-Pearson method for each treatment group by cohort using PPS for PCR-corrected ACPR and FAS for uncorrected ACPR.

Data will be handled as follows:

- Treatment failures after 7 days (i.e., Study Day 8) due to new infections based on PCR genotyping are not considered as failure for PCR-corrected analyses.

- For uncorrected ACPR, patients will be treated as failure on and after the visit when a reinfection with *P. falciparum* or other species is detected (which might be either recrudescence or a new infection).
- Patients who received rescue medication for the treatment of *P. falciparum* malaria (except for the treatment of a new infection) will be considered treatment failures. Patients who received other concomitant medication having an effect on malaria for reasons other than rescue therapy e.g., for the treatment of *P. vivax* (e.g., primaquine, certain antibiotics (sulfonamides, tetracycline, etc.) will be considered in the analysis as if they had not taken the drug.
- Patients will be counted as failure at a visit (e.g. Study Day 15, etc.) if (a) they did not have a parasite count, i.e., missing parasite count at that visit unless these patients could be classified as cured based on absence of parasitaemia (parasite count = 0) at a later time (e.g., Study Day 29), or (b) they did not have valid PCR evaluations at baseline and the visit if parasitaemia was present at that time (e.g., Study Day 15).
- For intermediate missing data, (a) once a patient experienced a treatment failure at a timepoint (eg. Day 15), the patient is considered as treatment failure at all later timepoints (eg. Day 29), (b) if a patient is considered as cured at a timepoint (eg. Day 29), the patient is considered as cured at earlier timepoints (eg. Day 15).

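### The per-protocol 80% medication rule has no exception for treatment failure, so infants stopped for Early Treatment Failure before the fifth dose would leave the PPS estimate of PCR-corrected ACPR

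*SAP*

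**What the plan says.** SAP 2.2 and Protocol 12.1 both define the PPS by three criteria, one being that the patient "took at least 80% of study medication". SAP 5.8 restates this as an exclusion: "Did take less than 80% of planned study medication (see Section 2.4.1".

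The denominator is in SAP 2.4.1: "Planned number of tablets in a treatment group = planned number of days of dosing x number of tablets to be administered per day" in that group. The worked example for dose level 2 is "3 (planned number of days of dosing) x 2 (number of tablets) x 2 (twice a day) = 12 tablets", and the formula is "Percentage of tablets taken will be calculated as Number of tablets consumed/Number of tablets planned x 100". Nothing shortens the planned course when treatment is stopped.

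Protocol 6.2.3 opens its list of ETF and late-failure criteria with "The following circumstances warrant discontinuation of study treatment (during the treatment period) and the implementation of rescue medication by the investigator". SAP 2.7.2.1 analyses the ACPR proportions "using PPS for PCR-corrected ACPR and FAS for uncorrected ACPR", and counts patients rescued for *P. falciparum* malaria (other than for a new infection) as failures.

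Other PPS criteria in SAP 5.8 do protect failures. The antimalarial-use deviation applies only to "Prohibited concomitant anti-malarial medication administered without experiencing ETF, LCF, LPF (PROH02". The two criteria on missing smears and undetermined PCR apply only to patients not already classed as non-responders before Day 8.

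**The concern.** Some infants would be excluded because of their outcome. An infant who meets ETF early in the course and is managed as Protocol 6.2.3 describes has study drug stopped, falls below 80%, and leaves the PPS. The number cured is unchanged while the denominator loses a failure, so the PPS cure proportion can only stay the same or rise. A failure counts at all later visits, so the loss carries through Days 15, 29 and 43. The ACPR sensitivity analysis in SAP 2.7.2.1.2 starts from the PPS and inherits the same loss.

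This looks like an oversight. The neighbouring criteria keep failures in the set, and the 80% criterion can then remove the earliest of them. The rule does not measure adherence in these infants either: dosing is directly observed by two staff (Protocol 6.6.1 and 6.7.2), and stopping for ETF follows the protocol. Key efficacy results also go to the Data Monitoring Committee at the interim assessments (SAP 2.12).

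**Working it through.** **Inputs.** Doses at 0, 8, 24, 36, 48 and 60 h (Protocol 6.1.4). Day 2 is 24 and 36 h, Day 3 is 48 and 60 h, Day 4 is 72 h (Protocol Table 8-1). ETF criteria from SAP 2.1.1.1. About 22 patients per cohort (SAP 3.1.2).

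**Step 1: the plan's own figure.** 3 days × 2 tablets × 2 per day = 12 tablets at dose level 2, as stated.

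**Step 2: the cut in doses.** 80% of 12 is 9.6, so at least 10 tablets are needed, which is 5 doses of 2. As percentages of 6 doses:

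| Doses taken | % of course | In PPS on this criterion |
|---|---|---|
| 3 | 50.0 | no |
| 4 | 66.7 | no |
| 5 | 83.3 | yes |
| 6 | 100 | yes |

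The cut is the same at dose levels 1 to 4, because tablets per dose cancel.

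**Step 3: which ETF events fall below it.**
- Day 2, danger signs or severe malaria with parasitaemia: at most 4 doses taken, so excluded if study drug is stopped before the 48 h dose.
- Day 3, the same signs or a count above Day 1: excluded only if stopped before the 48 h dose. Table 8-1 puts the 48 h film and the 48 h dose in the same column, so this depends on the film being acted on before the dose. After that dose the infant has 83.3% and is kept.
- Day 4, all criteria: the last dose was due at 60 h, so an infant dosed as planned is kept as a failure.

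**Step 4: effect on the PPS proportion.** The documents give no ETF rate, so the number of early stops, k, is assumed. With n = 22 otherwise eligible infants and everyone else cured, the rate is (22 − k)/22 if these infants are kept and (22 − k)/(22 − k) if they are dropped. The 95% Clopper-Pearson limits for x of n are the 2.5% quantile of Beta(x, n − x + 1) and the 97.5% quantile of Beta(x + 1, n − x), with upper limit 100% when x = n.

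| k | Kept as failures | Dropped (current rule) | Difference |
|---|---|---|---|
| 0 | 22/22 = 100% (84.6–100) | 22/22 = 100% (84.6–100) | 0 |
| 1 | 21/22 = 95.5% (77.2–99.9) | 21/21 = 100% (83.9–100) | 4.5 points |
| 2 | 20/22 = 90.9% (70.8–98.9) | 20/20 = 100% (83.2–100) | 9.1 points |

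If one later failure is added, k = 1 gives 20/22 = 90.9% kept against 20/21 = 95.2% dropped, and k = 2 gives 19/22 = 86.4% against 19/20 = 95.0%.

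**The case against.** The strongest reply is that a minimum-exposure rule is ordinary in a per-protocol set, and that the plan already has analyses that keep these infants. SAP 2.7.2.1.1 estimates PCR-corrected ACPR by Kaplan-Meier in the FAS at Days 29 and 43 with treatment failure as the event, and uncorrected ACPR uses the FAS. In the one-stop illustration, without censoring, the Kaplan-Meier estimate is 21/22 = 95.5%, so a gap between the two sets would show the exclusion. PCR-corrected ACPR is also secondary, with no prespecified hypothesis (SAP 2.7.2).

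This limits the consequence but does not remove the fault. Day 15 has no specified FAS estimate of PCR-corrected ACPR, though it could be read off the plotted curve. Two PCR-corrected results could also differ through set membership alone.

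A reader might go further and infer that the rule removes every infant stopped for ETF, or the worst failures. The documents do not support either. Step 3 shows that stops after the fifth dose and Day 4 ETF after full dosing stay in. The text establishes early timing, not greater severity.

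**Conclusion.** The point holds for stops before the fifth dose. Following the plan as written, an infant stopped for ETF with four or fewer doses taken (66.7% or less) is excluded from the PPS because treatment failed. If any such stops occur, the PPS proportion for PCR-corrected ACPR at Days 15, 29 and 43, and the PPS-based sensitivity analysis, are biased upwards.

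The size is conditional: 4.5 points for one stop and 9.1 for two, assuming 22 otherwise eligible infants with all others cured. It would be wrong to conclude that the trial's cure rate is inflated. That needs such stops to happen, and the documents give no rate.

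The primary artemether Cmax analysis uses the PK set and is unaffected. Only its PPS sensitivity analysis (SAP 2.5.4) shares this set.

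**What to change.** In SAP 2.2 and 5.8, and in Protocol 12.1 at the next amendment, state that the 80% criterion does not exclude patients whose study drug was stopped because they met ETF, and that they count as failures at all visits. The clause should say whether the site's or the central slide reading identifies ETF, since Protocol 8.3 derives efficacy endpoints from the central one. This changes the analysis only.

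Computing the percentage against doses due up to the stop is not an equivalent alternative. An infant who missed earlier doses and then met ETF would be kept by the exception but could still fall below 80% of doses due.

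The clause does not reach infants rescued after vomiting a replacement dose (Protocol 6.7.2), who can also fall below 80%. The sponsor should say how they are handled.

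Cost: one clause and a small change to the PPS derivation, with no new data, settled before PPS exclusions are fixed at database lock. The protocol text needs a written amendment (Protocol 14.1). The reported PPS cure rate may be slightly lower, and the PPS sensitivity analysis of artemether Cmax would gain any of these patients with a Cmax value.
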